4. ABBREVIATIONS

AE	Adverse Event
ALT	Alanine Aminotransferase
ASA	American Society of Anesthesiologists
AST	Aspartate Aminotransferase
AT	Anti-Thrombin
ATC	Anatomical Therapeutic Chemical
BIL	Bilirubin
BUN	Blood Urea Nitrogen
CA	Competent Authority
CRA	Clinical Research Associate
CRO	Contract Research Organization
CRP	C-reactive Protein
DSMB	Data Safety Monitoring Board
e-CRF	Electronic Case Report Form
ESR	Erythrocyte Sedimentation Rate
EU	European Union
GCP	Good Clinical Practice
GMP	Good Manufacturing Practice
Hb	Hemoglobin
HC	Hematocrit
HD	Hospital Discharge
ICH	International Conference on Harmonization
ICU	Intensive Care Unit
IEC	Independent Ethics Committee
INR	International Normalized Ratio
IP	Investigational Product
IRB	Institutional Review Board
ITT	Intention-to-treat
IU	International Unit
LDH	Lactate Dehydrogenase
LLT	Lowest Level Term
LOS	Length of Stay
MCH	Mean Cell Hemoglobin
MCHC	Mean Cell Hemoglobin Concentration
MCV	Mean Corpuscular Volume
MedDRA	Medical Dictionary for Regulatory Activities
MRI	Magnetic Resonance Imaging
OR	Operating Room
PCL	Poly-Caprolactone
PEG	Polyethylene Glycol
PhV	Pharmacovigilance

PLA	Poly-Lactide Acid
PLT	Platelets
QPPV	Qualified Person Responsible for Pharmacovigilance
RA	Regulatory Authority
RBC	Red Blood Cells
SAE	Serious Adverse Event
SAP	Statistical Analysis Plan
SGOT	Serum Glutamic Oxaloacetic Transaminase
SGPT	Serum Glutamic Pyruvic Transaminase
SOP	Standard Operating Procedures
SUSAR	Suspected Unexpected Serious Adverse Reaction
TAH	Topical Absorbable Hemostats
TBS	Target Bleeding Site
TMF	Trial Master File
TTHP	Time to Hemostasis from First Product Application
TTHR	Time to Hemostasis from Patient Randomization
US	United States
U.S.A.	United States of America
WBC	White Blood Cells
WHO	World Health Organization

5. INTRODUCTION

The success of any surgical procedure is based on adequate hemostasis (ref. 1). Ineffective local hemostasis is the major cause of bleeding during surgery, but many other causes may be involved.

During surgery or in the surgical management of trauma, Investigators encounter bleeding from a variety of tissue types. The selection of appropriate methods or products for the control of bleeding is dependent upon many factors, which include but are not limited to bleeding severity, anatomical location of the source and the proximity of adjacent critical structures, whether the bleeding is from a discrete source or from a broader surface area, visibility and precise identification of the source and access to the source. Tissue type and fragility/friability, coagulation system status and patient stability are also factors for consideration.

Major bleeding can be controlled by standard surgical techniques, such as stitches, ligatures, or clips. Chemical, thermal, and mechanical procedures can be used during surgery to achieve hemostasis, especially when diffuse hemorrhages occur. Surgical tools such as electrocautery, argon beamer, or laser are often useful. However, sometimes these methods do not achieve satisfying results, generating medical consequences and related costs (ref. 2).

Many products have been developed as adjuncts to hemostasis in bleeding situations where traditional methods such as suture, clips or energy-based coagulation are ineffective or impractical (ref. 3). These products include topical absorbable hemostats (TAH) such as oxidized regenerated cellulose, gelatin in various forms with or without a topical thrombin solution, and collagen powder, as well as biologically active topical hemostatic products (topical thrombin solutions, fibrin sealants, fibrin patches, etc.) and a variety of synthetic topical sealants (ref. 4-7).

The products that can be used during surgery may be classified as topical hemostats, sealants, and adhesives (ref. 3). Hemostats can clot blood. Sealants can create sealing barriers. Adhesives bond tissue together. Collagen, gelatin, and cellulose are hemostatic agents.

The term “fibrin sealant” denotes a product containing coagulation factors, to be administered topically to produce a fibrin clot. Typical fibrin sealant products contain human fibrinogen, as a substrate of the clot and biologically active thrombin, which converts the fibrinogen to fibrin.

The intended benefit of the topical fibrin sealant application is to support local hemostasis, or “gluing” together of surfaces of injured tissues in order to obtain adaption or sealing of surfaces, to support sutures, or to improve repair and healing. Fibrin sealants have been used to support local hemostasis in surgical situations where tight tissue sealing is required, and the usage of other conventional surgical hemostatic means is not possible. Usage of this type of products is therefore particularly justified in surgical procedures involving parenchymal organs such as liver and lung, and/or where rapid reliable hemostasis is required.

Most TAH and fibrin sealant products are not as effective in the presence of active and/or brisk bleeding since the lack of sufficient adhesion strength allows forceful bleeding to simply “float” the products away from the bleeding tissue, prior to the achievement of full hemostasis. Fibrin sealants lack the mechanical strength needed to withstand the force of active hemorrhage and are not indicated for use in such settings. Investigators regularly encounter active and/or brisk bleeding for which traditional methods of control are ineffective or are impractical and for which currently available adjunctive products perform unsatisfactorily. In these instances, Investigators need to use a variety of methods and products, frequently sequentially, to control the bleeding. This can include prolonged surgical packing.

Fibrin patches are thought to be useful as hemostats in cases of active and/or brisk bleeding. The current approved fibrin patches include EVARREST® and TACHOSIL®. Both products are expensive. There is still a need for more cost- effective products or techniques to rapidly control active and/or brisk bleeding when treatment with conventional surgical techniques or conventional adjunctive hemostatic products is either ineffective or impractical.

Sealantum Medical Ltd. has developed a new product, sFilm-FS, aimed to help controlling of body fluid leakage in general surgery procedures, therefore proposing its use as an adjunct to hemostasis and/or sealing. sFilm-FS has been developed to help Investigators controlling hemorrhage and does not require a dry surgical surface for effective application. sFilm-FS is a cost-effective product as the quantities of fibrin sealant embedded into the product are minimal. sFilm is a transparent flexible product, therefore increasing its ease of use and allowing Investigators to see the target bleeding site through the application.

sFilm-FS is currently intended to be used as an adjunct to hemostasis in liver bleeding during elective surgery, when control of bleeding by standard surgical methods of hemostasis (such as suture, ligature, cautery) is ineffective or impractical.

5.1. Product Description

sFilm-FS is a sterile bio-compatible bio-absorbable patch which consists of a polymeric film composed of a tri-block polymer (device component) containing Polyethylene Glycol (PEG) Poly-Caprolactone (PCL) and Poly-Lactide Acid (PLA), embedded with lyophilized powders of Human Fibrinogen, Human Thrombin (biological components) and calcium chloride. The composition of sFilm-FS is presented in Table 1.

Table 1: sFilm-FS Composition

Component	Amount/Patch*	Function
Co-Polymer Film:		
Polyethylene Glycol (PEG) (mg)	66 ± 3.6	Backbone hydrophilic component
Poly-Caprolactone (PCL) (mg)	153.3 ± 8.4	Backbone hydrophobic component
Poly-Lactide acid (PLA) (mg)	5.7 ± 0.3	Backbone hydrophobic component
Indigo Blue (μg)	4.5 ± 2	Dye component
Coating:		
Human Fibrinogen (mg)	21.0 ± 0.5	Clotting component (substrate)
Human Thrombin (IU)	24.0 ± 0.5	Clotting component (enzyme)
CaCl ₂ (mg)	1.2 ± 0.3	Cofactor

¹ Based on the weights of the components in the final patch; patch size 5 x 5 cm²

The polymeric film consists of a di-block polymer containing PEG and PLA, with the permutations to the polymer microstructure by addition of PCL to the synthesis mixture, which extends the degradation rate of the co-polymer. All the co-polymer components (PEG, PCL, and PLA) are used in approved implantable devices (CoSeal®, Monocryl®, Artelon®, Ligafix®, PREVADH®).

The lyophilized biological components (Human Fibrinogen and Human Thrombin) are licensed components (CSL Behring GmBH). The Human Fibrinogen is identical to the RiaSTAP product (STN # 125317/0, CSL Behring) used for treatment of acute bleeding in patients with congenital fibrinogen deficiency, afibrinogenemia and hypofibrinogenemia. The Human Thrombin component is approved for further manufacturing use (BLA FFMU STN #125357/0) and is being used in the manufacture of fibrin sealants. Human Fibrinogen and Human Thrombin components are equivalent to endogenous proteins, with well understood functional effect (ref. 8-10). These components are included in sFilm-FS in a relatively low amounts, compared to the amount of the same components used in EVARREST® or TACHOSIL® fibrin patches (see Table 2 below).

Table 2: Fibrin Sealants Components*

Product	Fibrinogen Amount* (mg/cm ²)	Thrombin Amount* (IU/cm ²)	App. Fib:Thr Ratio (mg : IU)
EVARREST®	8.6	37	1:4
TACHOSIL®	5.5	2.0	2:1
sFilm-FS	0.84	0.96	1:1

* Refers to nominal amounts

** In EU SmPC the nominal numbers are 8.1 mg/cm² for Fibrinogen and 40 IU/cm² for Thrombin

The polymeric film is durable, flexible, transparent, and non-permeable to body fluids. sFilm-FS is biodegradable. Within sFilm-FS manufacturing process, the lyophilized biological components are embedded onto the polymeric film using a unique printing method.

Preclinical safety and toxicological evaluations of sFilm-FS and its constituent components have uncovered no concern for risks of particular severity or seriousness and support the use of the product in the proposed clinical trial. See Investigator's Brochure for further details.

6. STUDY OBJECTIVES

The primary objective of this study is to evaluate the safety of sFilm-FS versus an active-comparator (TACHOSIL®) when used as adjunct to conventional hemostatic techniques during elective surgery in which liver bleeding is encountered.

The secondary objective of this study is to preliminarily evaluate the hemostatic efficacy of sFilm-FS in controlling liver bleeding during elective surgery.

7. STUDY DESIGN

7.1. Overview of Study Design

This is a Phase I/II randomized, prospective, controlled, multi-center, open-label, two-arms study evaluating the safety and preliminary efficacy of sFilm-FS in controlling liver bleeding during elective surgery, when conventional methods of control are ineffective or impractical. Patients will be randomized with a 1:1 allocation ratio to either sFilm-FS (investigational product) or TACHOSIL® (active-comparator).

The surgical procedure will be performed as per standard of care at the investigational site. A target bleeding site (TBS) will be identified intra-operatively by the Investigator following transection of the hepatic parenchyma.

Target Bleeding Site (TBS) is defined as the first bleeding site in which conventional methods of bleeding control (i.e., suture, ligature, cautery) are ineffective or impractical. The TBS must be a site where occlusion of the injured surface blood vessels is required to achieve hemostasis. It must be possible to cover the TBS adequately, with an appropriate overlap, using a single unit of product (sFilm-FS or TACHOSIL®). This excludes bleeding from large defects in large arteries or veins requiring repair.

The TBS is the only site or region to be evaluated for hemostasis in this clinical study. If additional bleeding sites/regions requiring a topical hemostatic product are identified after the treatment of the initial target bleeding site, these bleeding sites should be treated with the same study medication according to the patient's randomization assignment, if clinically appropriate. These areas will not be assessed for hemostasis, but information will be collected.

Once the TBS has been identified (intra-operatively), the Investigator will immediately enroll and randomize the Patient into one of the following treatment arms:

- **Group A** (investigational product): sFilm-FS will be applied at the target bleeding site immediately after conventional methods of control have been exhausted. The sFilm-FS should adequately cover the entire target bleeding site. After application of sFilm-FS, the Investigator will immediately apply manual compression continuously for at least 2 minutes. A surgical sponge may be used to assist in providing adequate pressure. Hemostasis will be assessed after carefully releasing the compression at the site. sFilm-FS should not be removed once bleeding has stopped. A maximum of 4 units of sFilm-FS may be used per patient.
- **Group B** (active comparator): TACHOSIL® will be applied at the target bleeding site immediately after conventional methods of control have been exhausted. TACHOSIL® should be applied as per the approved prescribing information, with a manual compression of at least 3 minutes. A maximum of 4 units of TACHOSIL® may be used per patient.

Patients will be then monitored for a total period of 6 months following surgery. Patients will be evaluated at study site at Screening Visit (Visit 1, between Day -21 and Day -1), Visit 2 (1 day before surgery), Visit 3 (Day 0, the day of surgery), Visit 4 (daily assessments post-surgery until the day before hospital discharge), Visit 5 (assessments post-surgery, the day of hospital discharge), Visit 6 (control visit 1; at 30 ± 3 days post-surgery) and Visit 7 (control visit 2; at 180 ± 14 days post-surgery). Monitoring of patients will include a list of evaluations, including vital signs, physical examination, blood, and urine sampling, MRI assessment, evaluation of antibodies for Human Fibrinogen and Human Thrombin, recording of adverse events, transfusion requirements and concomitant medications, as indicated in the Schedule of Assessments. Efficacy assessment will be evaluated intra-operatively by evaluation of hemostasis before patient's surgical closure.

The study will be monitored by an independent Data Safety Monitoring Board (DSMB). The DSMB will have responsibility for the review of data and identification of any potential safety issues throughout the study. If necessary, the DSMB will make recommendations regarding protocol revisions, and will recommend whether the study should proceed based on the safety data considering established stopping rules.

7.2. Number of Patients

The sample size will be of 30 patients completing the study. 15 patients will be included in the experimental treatment arm (Group A) and 15 patients in the active-comparator arm (Group B) to allow an adequate comparison between treatments. Dropped patients during the course of the study will be replaced.

7.3. Study Discontinuation

7.3.1. Patient Discontinuation Criteria

All randomized patients should be encouraged to remain in the study until they have completed the follow-up visits. Patients may discontinue participation in the study at any time and for any reason. However, if the patient decides to discontinue participation in the study, the reason must be documented when possible. Reasons for early withdrawal include, but are not limited to:

- Consent withdrawn by the patient;
- Patient refusal to complete study visits and/or procedures;
- Lost-to-follow-up: a certified letter will be sent to the patient at their last known address, after a minimum of three attempts to reach the patient by telephone have failed. If communication via certified letter is unsuccessful, the patient will be considered lost-to-follow-up.

Patients who discontinue from the study prematurely will be replaced.

Note: The eCRF should be completed as far as possible and all data relating to the patient prior to discontinuation will be made available to the Sponsor or its designee and DSMB.

7.3.2. Stopping Rules

If one of the following occurs during the enrollment period of patients receiving the test article (sFilm-FS) the study will be immediately suspended:

- Three or more patients developed a suspected unexpected serious adverse reaction (SUSAR) caused by a TBS post-operative re-bleeding (not requiring surgery re-intervention);
- Two or more patients had a TBS re-bleeding events following final observation period that required surgery re-intervention;
- Three or more patients developed other possible serious adverse reactions like thromboembolic events or severe allergic reactions.
- Three or more patients develop serious unanticipated or unexpected local reactions (serious adverse events) such as:
 - Signs of local reactions affecting the spleen and liver (persistent pain in the area of the application that is unanticipated or unexpected)
 - Persistent unanticipated and unexpected Systemic inflammatory response syndrome (SIRS), defined with at least two of these conditions: body temperature over 38 or under 36 degrees Celsius, heart rate greater than 90 beats/minute or respiratory rate greater than 20 breaths/minute or partial pressure of CO₂ less than

- 32 mmHg, leucocyte count greater than 12000 or less than 4000 /microliters or over 10% immature forms or bands
- Reactions on other local organs such as adhesions and reactions impacting the intestinal tract etc., assessed as being due to local reactivity. This would be diagnosed as a bowel obstruction that is unanticipated.

These stopping rules only apply to the investigational treatment group (Group A). The active-comparator group (Group B) patients should be followed according to the Investigator's standard practice as clinically appropriate.

After study suspension, the Data Safety Monitoring Board (DSMB), together with the Sponsor, will review the data and decide whether to continue or terminate the study.

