7.3.3. Premature Termination of the Study

The Sponsor reserves the right to discontinue the study at any time. Premature termination of the study can be conducted voluntary by the Sponsor or by a regulatory agency at any time during the course of the study. Premature termination of the study can also be requested by the independent DSMB.

If the study is terminated for any reason, every attempt will be made to complete a follow-up visit, in which the patient will have a further blood sample taken for hematology and coagulation tests and a physical examination. In case of an adverse event, the patient will be followed-up until the event has been resolved or has been stabilized and no further change is expected.

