7.4. Data Safety Monitoring Board (DSMB)

A DSMB will be convened for this study and will review the results of the trial at regular intervals, including safety reports, to protect patients participating in the study.

DSMB will make recommendations to the Sponsor regarding protocol revisions and will recommend whether the study should be closed prematurely based on safety concerns. For this, DSMB will receive timely all reports of patients with adverse events and patients discontinued from the study, with particular attention to patients who had intra-operative TBS re-bleeding events following final observation period that required re-intervention, patients with serious adverse event related to TBS post-operative re-bleeding, and patients who developed a suspected unexpected serious adverse reaction (SUSAR) following product application.

DSMB will operate based on a DSMB Charters. The charter will define the primary responsibilities of the DSMB, its relationship with other trial components, its membership, and the purpose and timing of its meetings. The charter will also provide the procedures for ensuring confidentiality and proper communication.

The DSMB will consist of at least three members, appointed by the Sponsor, who have agreed to serve. The DSMB includes experts in or representatives of the fields of relevant clinical expertise and clinical trial methodology.

At the first meeting of the DSMB, the individual members will vote to determine who will serve as the Chairperson. The Chairperson is responsible for overseeing the meetings and developing the agenda of DSMB meetings. The chairperson is the contact person for the DSMB. Periodic reports from the DSMB will be provided to the Sponsor. The Sponsor (or its designee), in turn, will submit these reports to the EC/IRB of each study investigational site in a timely manner.

HEM-01-17 Study is in compliance with the Guideline on Data Monitoring Committee, EMEA/CHMP/EWP/5872/03 Corr. of 27-7-2005.

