The time of application will be considered **TP-01** and will be recorded as such. If the sFilm-FS is to be used, do not moisten the product prior to application, as the product will be activated immediately. TACHOSIL® should be used in accordance with the approved Prescribing Information.

Following product application, manual compression will be applied and will be maintained for at least 2 minutes for sFilm-FS and for at least 3 minutes for TACHOSIL®, until examination of TBS. The Investigator may use a surgical sponge (laparotomy pad or surgical gauze) to assist in providing adequate pressure to stem all bleeding over the entire treated surface area at the TBS. Hemostasis will then be assessed by carefully releasing manual compression and removing the surgical sponge (if used) without disturbing the hemostasis product. The product unit should be left in place once it adheres to organ tissue.

In case hemostasis is not achieved within 2 minutes (for sFilm-FS) or 3 minutes (for TACHOSIL®), the surgeon will wait 2 additional minutes applying additional pressure on the gauze before carefully releasing manual compression and checking again.

Hemostasis will be assessed at 2 (for sFilm-FS only), 3, 5, 7 and 10 minutes following product application. These time points will be recorded as **TP-02**, **TP-03**, **TP-05**, **TP-07** and **TP-10** respectively.

Re-treatment: If the surgeon is not satisfied with the placement of the patch, or if hemostasis is not achieved, or if during the subsequent observation period bleeding requiring treatment recurs, the

Investigator may decide to apply an additional product unit as specified above. In this case, the already applied product unit should not be removed, unless it did not adhere to the TBS.

The time point of product re-application will be recorded as **TPR-01**. After re-treatment application, manual compression must be applied for at least 2 (for sFilm-FS) or 3 minutes (for TACHOSIL®, as described above. Hemostasis will then be assessed following product re-application at any time-points within the original 10 minutes observation period (**TPR-02**, **TPR-03** or other) and until site closure. A minimum of 5 minutes observation period at the TBS has to take place before site closure. The time followed by 5-minutes observation period to assess hemostasis will be recorded.

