13.4. SAE Reporting

Any SAE, whether deemed study medication-related or not, must be reported to the Local Clinical Management (CRA and Sponsor Qualified Person Responsible for Pharmacovigilance (QPPV)) within 24 hours after the Investigator has become aware of its occurrence, using the SAE form. The SAE form completion and reporting must not be delayed even if all of the information is not

available at the time of the initial contact. The local Clinical Management will forward the report to the Sponsor's QPPV who will handle all the safety reports.

SAE originated in this study should be sent to:

seQure Life Sciences

PhV Officer

[contact]

[contact]

Additional information (follow-up) about any SAE unavailable at the initial reporting should be forwarded by the site within 24 hours of the information becoming available to the Local Clinical Management.

The following information should be provided on the SAE form to accurately and completely record the event:

- Investigator Name and Investigational site Number.
- Patient Number.
- Patient initials.
- Patient Demographics.
- Clinical Event:
 - ✓ Description.
 - ✓ Date of onset and end date.
 - ✓ Severity.
 - ✓ Treatment.
 - ✓ Relationship to study drug (causality).
 - ✓ Action taken regarding study drug (none / dose delayed / dose reduced / product withdrawn).
 - ✓ Outcome (completely recovery; sequelae; improvement; persistent; death; unknown).
- If the AE results in Death:
 - ✓ Cause of death (whether or not the death was related to study drug).
 - ✓ Autopsy findings (if available).
- Medical History case report form (copy).
- Concomitant Medication case report form (copy).
- Any relevant reports (laboratory, discharge, X-ray, etc).

SAE must be collected and reported regardless of the time elapsed from the last study. For both initial and follow-up SAE reports the Local Management forwards this information to PhV responsible within 48 hours.

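### Stopping rule 1 drops re-operated patients from its count, so three SUSAR re-bleeds suspend the study but the same three with one re-operation do not

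*Protocol*

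**What the plan says.** Protocol section 7.3.2 lists four events, any one of which suspends the study immediately. They apply to Group A (sFilm-FS) only and during the enrolment period.

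- Rule 1: "Three or more patients developed a suspected unexpected serious adverse reaction (SUSAR) caused by a TBS post-operative re-bleeding (not requiring surgery re-intervention").
- Rule 2: "Two or more patients had a TBS re-bleeding events following final observation period that required surgery re-intervention".
- Rule 3: three or more patients with other serious reactions; the examples are thromboembolism and severe allergy.
- Rule 4: three or more patients with serious unexpected local reactions; the examples are persistent pain, systemic inflammatory response, and adhesions or bowel obstruction.

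No rule adds rule 1 and rule 2 events together. After a suspension the DSMB and the sponsor "review the data and decide whether to continue or terminate the study".

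Other sections also bear on this. SAEs are reported "within 24 hours after the Investigator has become aware of its occurrence" (section 13.4). Under section 7.4, "DSMB will receive timely all reports of patients with adverse events and patients discontinued from the study", with particular attention to three groups, one of which is patients with an SAE related to post-operative TBS re-bleeding. Section 7.3.3 adds: "Premature termination of the study can also be requested by the independent DSMB". The SAP (section 3.1) refers back to section 7.3.2 and adds no combined rule.

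**The concern.** A stopping boundary should not become harder to reach when a patient's outcome gets worse. Rule 2 has the lower threshold (two against three), so the protocol itself treats re-operation as the graver event. Yet the parenthesis in rule 1 means that a patient whose SUSAR re-bleed goes on to re-operation leaves the rule 1 count and enters a separate count that may stay at one.

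Safety is the primary objective, bleeding at the TBS is the first adverse event type named in the primary endpoint, and section 7.3.2 holds the only pre-set limits for suspension. At stake is whether those limits act in the order of severity that they imply.

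**Working it through.** **Plan's own figure.** There is none to reproduce: the documents give no operating characteristics for the stopping rules, and no re-bleed rate, re-operated share or SUSAR fraction.

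**Step 1: the logic, which needs no rates.** Let a = patients with a SUSAR re-bleed and no re-operation, r = patients re-operated for a TBS re-bleed, and c = those among r whose re-bleed is also a SUSAR.

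- As written: suspend if a ≥ 3 or r ≥ 2.
- With re-operated SUSARs kept in rule 1: suspend if a + c ≥ 3 or r ≥ 2.

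| Pattern (all SUSARs) | Rule 1 count | Rule 2 count | As written | Corrected |
|---|---|---|---|---|
| Three, none re-operated | 3 of 3 | 0 of 2 | Suspend | Suspend |
| Three, one re-operated | 2 of 3 | 1 of 2 | No suspension | Suspend |
| Three, two re-operated | 1 of 3 | 2 of 2 | Suspend | Suspend |

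The two versions can differ only when r ≤ 1, so c ≤ 1, and a + c reaches three while a does not. That leaves one outcome: a = 2, r = 1, with the re-operated patient a SUSAR. Rules 3 and 4 do not fill it. Rule 3 is for other reactions, and counting TBS re-bleeds under rule 4 would make rule 1 redundant.

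**Step 2: size, on assumed rates.** Take n = 15 (planned size of Group A, section 7.2), p = serious TBS re-bleed rate, s = re-operated share, f = fraction of re-bleeds that are SUSARs. With f = 1, the gain in suspension probability is the probability of that one outcome:

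P(a = 2, r = 1) = [15! / (2! 1! 12!)] × [p(1−s)]² × (ps) × (1−p)¹² = 1365 × p³ × s(1−s)² × (1−p)¹²

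Example, p = 0.10 and s = 1/3: 1365 × 0.001 × 0.1481 × 0.2824 = 0.057.

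| p | Gain, s = 1/5 | Gain, s = 1/3 | Gain, s = 1/2 | Suspension probability, s = 1/3, written → corrected |
|---|---|---|---|---|
| 0.02 | 0.0011 | 0.0013 | 0.0011 | 0.0054 → 0.0066 |
| 0.05 | 0.012 | 0.014 | 0.012 | 0.038 → 0.051 |
| 0.10 | 0.049 | 0.057 | 0.048 | 0.157 → 0.214 |
| 0.20 | 0.096 | 0.111 | 0.094 | 0.516 → 0.628 |

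The factor s(1−s)² peaks at s = 1/3, so other shares give less: at p = 0.10, 0.017 for s = 0.05 and 0.012 for s = 0.8.

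**Step 3: only some re-bleeds are SUSARs.** With f = 0.5 and s from 1/5 to 1/2, the gain is about 0.002 at p = 0.05, 0.008-0.011 at 0.10 and 0.024-0.038 at 0.20. At p = 0.10 and s = 1/3, the probability of a = 2, r = 1 is 0.022. The re-operated patient is a SUSAR in half of that, so the correction catches 0.011.

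**Step 4: patients treated.** Following the arm patient by patient, with immediate reporting, f = 1 and s = 1/3, the mean number treated with sFilm-FS, written v corrected, is 14.978 v 14.974 at 2%, 14.85 v 14.80 at 5%, 14.33 v 14.09 at 10% and 12.45 v 11.66 at 20%.

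**The case against.** **Separate tiers are legitimate.** Any set of separately tested rules leaves some combinations below every threshold. That is true, but here the missed combination is a worsened form of one that is caught, which tiering does not require.

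**The parenthesis may be meant loosely**, as saying that re-operation need not have occurred. That would close the gap. Beside a separate rule for re-operated cases, exclusion is the more natural meaning; if the loose sense was intended, the proposed wording simply states it.

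**The DSMB sees these events anyway.** This stands and limits the point. The particular attention that section 7.4 directs to SAEs from post-operative TBS re-bleeding has no re-operation limit and no SUSAR condition, so all three patients would be in view. A suspension itself leads only to review.

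**The size is small.** This also stands: about 0.01 at a 5% re-bleed rate even if every re-bleed is a SUSAR, and less at lower rates. No document supports the 10-20% rates at which it grows.

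**Two stronger readings should be resisted.**

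- A reader might infer that any re-operated re-bleed added to two SUSARs is worse than three SUSARs. Rule 2 has no SUSAR condition, and SAP section 3.3.2 recognises that re-bleeding can follow movement of the patch by the surgeon or another external factor. Three suspected product reactions may be a stronger signal than two plus a mechanical re-operation. The ordering is clearly inverted only when the re-operated case is also a SUSAR.
- A reader might infer that rule 2 covers intra-operative events only, because section 7.4 speaks of "intra-operative TBS re-bleeding events following final observation period that required re-intervention" and section 11.1.3 says "A minimum of 5 minutes observation period at the TBS has to take place before site closure". Post-operative re-operations would then count under neither rule 1 nor rule 2. But rule 2 itself carries no such limit, the phrase comes from a list of items for DSMB attention, and such events could arguably count under rule 3. This is an ambiguity to clear up, not a second gap to quantify.

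**Conclusion.** The point holds, at minor severity. As worded, section 7.3.2 suspends the study for three SUSAR re-bleeds without re-operation and does not when one of those three patients is re-operated. That follows from the text, given the natural reading of the parenthesis, and needs no assumed rate.

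The size does rest on assumptions. With 15 sFilm-FS patients, every serious re-bleed a SUSAR and a re-operated share of one fifth to one half, the correction adds about 0.001 to the suspension probability at a 2% re-bleed rate, 0.01 at 5%, 0.05-0.06 at 10% and 0.09-0.11 at 20%. It adds less if only some re-bleeds are SUSARs.

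The loss is an automatic, temporary pause. The documents do not support a claim that such patients would go unreviewed.

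**What to change.** In rule 1, replace the parenthesis with *whether or not surgical re-intervention was required*. Keep rule 2 at two or more, and state that it covers any TBS re-bleed after the final observation period that requires re-operation, including post-operative ones.

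This closes the gap for re-operated re-bleeds that are SUSARs. One that is not a SUSAR would still count only under rule 2. If the sponsor wants it to count towards the three as well, rule 1 should read: *three or more patients with either a SUSAR caused by TBS post-operative re-bleeding or a TBS re-bleed requiring re-operation*. That is a choice for the sponsor and the DSMB.

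The cost is one line in each of two rules, repeated in the DSMB charter if the charter restates them. No new data are needed. The downside is a slightly higher chance of a reversible suspension, by the amounts given above if only the parenthesis is replaced. The wider rule adds more when some re-bleeds are not SUSARs: 0.022 rather than 0.011 at a 10% rate, one third re-operated and half SUSARs.

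The rules act only during enrolment, and SAP section 3.1 describes randomization in the past tense, so the time for an amendment may have passed. If so, the wording should be corrected in the next protocol that reuses these rules.
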